**Figure 2.**

This device is part of the PhySens™ ecosystem that includes a variety of sensor types designed to monitor important aspects of daily life such as sleep, exercise, cognitive state, gait, etc. The data obtained from the PhySens-IMM will be used to inform and complement the data collected from the Walkasins device and the functional assessments. (See [IDL's website](#) for more detailed information regarding this device.)

Ultra-Wideband (UWB) Real Time Location System

As a truth source, subject position will be tracked using the MDEK1001 Ultra-Wideband Real Time Location System, manufactured by Qorvo (formerly Decawave). This system uses a set of static “Anchor Nodes” positioned around the testing area to determine the relative position of “Tag Nodes” as seen in the figure 3 below.

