The primary aim of this pilot study is to investigate the effect of lower-leg mechanical tactile sensory stimulation on the gait speed and balance function of participants with mild cognitive impairment as measured by the SLUMS Examination. We hypothesize that participants will increase their gait speed and improve clinical outcomes, suggesting less reliance on compensatory executive control⁹ when their Walkasins are turned on.

Pilot Study Design

Research Design

This pilot study will collect data from individuals with mild cognitive impairments who consent to participate in one assessment session. It will employ a pre- and post-test study design to evaluate whether wearing active Walkasins (i.e., Walkasins turned on) improves the participants' gait speed and other clinical outcomes of gait and balance function.

Study Site

The Pillars at Prospect Park, a senior living community located in Minneapolis-St. Paul, has agreed to allow RxFunction to recruit its residents and to use space at its facility to conduct this pilot study. The Pillars will not receive any funds for this project, and its employees will not be engaged in any research-related activities aside from potentially informing prospective participants about the availability of the research, providing prospective participants with the study team's contact information, and/or obtaining the prospective participants' permission for the study team to contact them.

Participant Selection

Up to 20 study participants will be enrolled in this pilot study. To participate, individuals must meet the following inclusion and exclusion criteria.

Inclusion Criteria

- Ambulatory person who is at least 65 years of age
- Ability to understand and provide informed consent: For this study we will assume participants are able to consent if they can satisfactorily answer the following questions:
 - How would you describe your brain health right now?
 - What is this study about?
 - If you decide to be in this study, what harm (risks) might occur?
 - Will this study mainly help you or others?
 - If you want to stop being in the study, when can you do this?
 - Can you please explain how you decided to participate in this study?
- Ability to perceive vibrations from the Walkasins Haptic Module
- Ability to complete the functional outcome measures without the use of an assistive device
- Foot size that allows the Walkasins to function appropriately

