The final assessment for eligibility is a four-meter timed walk excluding an initial two meters to allow for acceleration. Participants will remain eligible for the pilot study if their gait speed is less than 1m/second. (At their discretion the investigator[s] may enroll individuals whose gait speed is slightly faster than 1m/second, provided they meet all other eligibility criteria.) This test may be repeated if necessary.

[figure not shown]
Participants who meet all eligibility criteria will then don a pair of Walkasins and the PhySens-IMM System. They will perform some brief balance exercises (i.e., sensory integration exercises) and then complete the following assessments with their Walkasins turned off and without the use of an assistive device:

- Short Physical Performance Battery (SPPB): The SPPB “is a composite measure assessing walking speed, standing balance, and sit-to-stand performance.” Research has shown it to be “predictive of an increased risk of falling” among other outcomes associated with older populations.¹² (Complete instructions for the SPPB are available at <https://geriatric toolkit.missouri.edu/SPPB-Score-Tool.pdf>.)
- Timed Up and Go (TUG): The TUG is part of the Centers for Disease Control-recommended STEADI test protocol for balance function.¹³ From a seated position in a standard armchair, the participant is asked to do the following:
 - 1) Stand up from the chair.
 - 2) Walk to a line on the floor 10 feet away normal pace.
 - 3) Turn.
 - 4) Walk back to the chair at normal pace.
 - 5) Sit down again.The tester will record the time taken from the command “Go” until the participant sits down again.
- Timed Up and Go Cognitive (TUG-COG): The TUG-COG is performed as described above; in addition, the participant is asked to count “backwards by threes from a randomly selected number between 20 and 100.”¹⁴ To standardize the assessment for this pilot study, the study team member who conducts the TUG-COG will use the same starting number for all participants (e.g., the same odd number for the first TUG-COG assessment and the same even number for the second TUG-COG assessment).

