After a five-minute break, study staff will then guide the participants through the same sensory integration exercises they performed before the first set of assessments. Participants will then retest participants on the same assessments with Walkasins turned on and without the use of assistive devices. Upon completion of the assessments with their Walkasins turned on, participants will remove their Walkasins and the PhySens-IMM System and complete the Falls Efficacy Scale (FES).¹⁵ The subjects’ participation in the study will then be over.

Pilot Study Duration

The pilot study will involve one visit that may last 1 to 1-1/2 hours. (A flow chart of the study visit appears on the following page.) We anticipate that all data collection will be completed within three months after study initiation.

Data Management and Quality Plan

Data Deidentification

Study staff will assign identification numbers to the participants' data, and they will use those numbers when analyzing the collected data.

Data Confidentiality, Storage, and Retention

All research team members will observe standard data confidentiality and security measures including, but not limited to, the following:

- Study staff will collect only the minimum identity information needed.
- Any portable electronic devices utilized in the study will be stored in secure locations when they are not in use.
- Physical and electronic access to the pilot study data will be limited to authorized personnel only.
- No information that can identify individual participants will appear in any publications or presentations that may result from analysis of the pilot study data.

Pilot study data will be retained indefinitely in a limited-access spreadsheet or spreadsheets. Any printed materials (e.g., consent forms) will be confidentially shredded when the period for their retention has passed (i.e., two years after study completion).

Data Quality

Data entry will occur directly as the study visits are conducted. Quality control measures to ensure data accuracy and integrity procedures for this pilot study include the following measures:

- Validation checks will be incorporated into cells as much as possible to help ensure that data entries are logically consistent with questions asked or tasks performed.
- No imputation methods will be used to infer missing values of any outcome measures.

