- Data collection forms will be reviewed for completeness and consistency. Errors will be corrected, following standard GCP procedures.

Data Sharing

RxFunction may share information from the pilot study with researchers at other companies or institutions in accordance with standard data sharing agreements that

protect the confidentiality of study participants. Only RxFunction company officers may approve data sharing agreements.

Sharing of Results with Participants

At its discretion RxFunction may share information from the study with participants, providing only their own data or via reports summarizing results on all participants if requested (e.g., through a newsletter or RxFunction website posting).

Statistical Analysis Plan

We will use descriptive statistics as well as regression analysis to investigate trends in changes for the various outcomes measured. Walkasins on versus off conditions will be compared using paired t-test as well as Wilcoxon Signed Rank Test for non-normally distributed data. Test of normality will be conducted using the Shapiro–Wilk test. In addition, we may conduct qualitative analyses on participants' comments to answer research questions.

Risks and Potential Benefits

Potential Benefits

There are no direct benefits to individuals who participate in this pilot study; however, we hope that the information gleaned through their participation will enhance our understanding of Walkasins' potential role in the treatment of gait difficulties experienced by individuals with mild cognitive impairments.

Pilot Study Risks and Their Mitigation

- The device being tested may distract the participants while they are walking and increase the risk of falling. To help prevent falling during the testing at the research site, a spotter will walk next to the participants to help them regain balance if a fall starts to occur.
- There is a very low chance that participants may find the device stimulations uncomfortable. If this occurs, the participants can decide if they wish to end participation in the pilot study.
- RxFunction personnel may request participants' medical information relevant to the study, but they will limit the data collected to the minimum necessary to conduct the study.
- There may be other unknown side effects that could occur.

Every effort will also be made to minimize potential risks by the following means:

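### The off/on gait-speed comparison is open to tester timing bias, and the planned UWB and IMU recordings that could check it are given no part in that comparison

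*Combined protocol and SAP*

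**What the plan says.** Pilot Study Aim and Hypothesis makes gait speed and balance the primary aim and predicts faster gait when the device is on. Study Visit Procedures fixes the sequence. Participants first "complete the following assessments with their Walkasins turned off and without the use of an assistive device". After a five-minute break they are retested on the "same assessments with Walkasins turned on and without the use of assistive devices". No random order, sham or masked assessor is described. Masking the participant would be hard in any case, because eligibility requires "Ability to perceive vibrations from the Walkasins Haptic Module".

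The assessments are the SPPB, TUG and TUG-COG. For the TUG, "The tester will record the time taken from the command" to start until the participant is seated again. The pace is self-selected, for example "Walk back to the chair at normal pace". The TUG-COG is done the same way with a counting task added. The SPPB includes walking speed, but its instructions are on an external sheet.

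Two instruments are described in the background:

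- The UWB section says "As a truth source, subject position will be tracked using the MDEK1001 Ultra-Wideband Real Time Location System". It gives up to 10 locations per second and a typical accuracy better than 10 cm, with positions logged to a laptop.
- The IMU section says that the sensor's data "will be used to inform and complement the data collected from the Walkasins device and the functional assessments".

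The Statistical Analysis Plan says "Walkasins on versus off conditions will be compared using paired t-test", with the Wilcoxon signed rank test for non-normal data. It names no outcome and mentions neither instrument.

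**The concern.** The tester can infer the device state from the stage of the visit and may know which result is hoped for. If start and stop are judged even slightly differently in the second block, the shift enters every paired difference with the same sign. It does not average out over participants, and no later analysis of the same times can remove it. A short walk is the most exposed, since a fraction of a second is a visible share of the time. The trial plans an independent position and motion record, but says nothing about using it to measure off/on speed or to check the tester's times.

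**Working it through.** The plan gives no effect size, SD, alpha or power, so there is no figure of its own to reproduce. What follows is an illustration.

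**Inputs from the documents.** Gait speed for eligibility is below 1 m/s, or slightly faster at discretion. Enrolment is up to 20. The TUG line is 10 feet away. UWB gives 10 Hz and 10 cm.

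**Assumptions.** The outcome walk is 4 m (the only 4 m walk in the text is the eligibility test, done before the device is put on). The systematic shift b is 0.1 to 0.2 s. SDs of paired differences are as shown. Two-sided alpha is 0.05. The 10 cm accuracy is treated as one SD.

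**1. False gain on a 4 m walk.** Gain = 4/(4/v − b) − v.

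| v (m/s) | true time (s) | b = 0.1 s | b = 0.2 s |
|---|---|---|---|
| 0.9 | 4.444 | 4/4.344 − 0.9 = 0.021 | 4/4.244 − 0.9 = 0.042 |
| 1.0 | 4.000 | 4/3.9 − 1.0 = 0.026 | 4/3.8 − 1.0 = 0.053 |

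At 0.7 m/s the gains are smaller: 0.0125 and 0.025 m/s.

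**2. What that does to the test.** With n = 20 a paired t-test is significant once the mean difference exceeds 0.47 SD of the differences. With no true effect, the noncentral t distribution gives the chance of a significant result favouring the device (nominal 2.5%) at 0.9 m/s:

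| SD of differences (m/s) | b = 0.1 s | b = 0.2 s |
|---|---|---|
| 0.05 | 42% | 95% |
| 0.10 | 14% | 44% |
| 0.15 | 8% | 22% |

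**3. The TUG.** The same 0.2 s shift gives 40%, 13%, 8% and 6% for assumed SDs of 0.5, 1.0, 1.5 and 2.0 s. In relative terms, the two legs total 20 × 0.3048 = 6.10 m. At 0.9 m/s walking alone takes 6.10/0.9 = 6.8 s, before standing, turning and sitting. So 0.2 s is at most 0.2/6.8 = 3% of the TUG, against 0.2/4.444 = 4.5% of the 4 m walk.

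**4. Error of a UWB-derived speed, per 4 m walk.**

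- Straight-line fit at 0.9 m/s, 45 samples, independent errors: 0.1/√(0.1² × 45 × (45² − 1)/12) = 0.1/8.71 = 0.011 m/s.
- Two end points only at 0.9 m/s: √2 × 0.1/4.444 = 0.032 m/s.
- End points plus 10 Hz sampling error: 0.025 m/s at 0.7 m/s and 0.037 m/s at 1.0 m/s.

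The range is thus about 0.01 to 0.04 m/s. Taking the end-point-plus-sampling figures, the contribution to the standard error of a mean paired difference with n = 20 is 0.025 × √2/√20 = 0.008 to 0.037 × √2/√20 = 0.012 m/s. This error is random with respect to the tester's expectations and shrinks with n; a consistent lean by the tester does not.

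**The case against.** Much of the opposing case stands.

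- A reader might infer that all tests are timed by hand by sponsor staff. The text says only that the tester records the TUG time. No stopwatch is mentioned, SPPB timing is on a sheet outside the documents, and collaborators may assist.
- A reader might infer that both instruments are confined to a supporting role. The sentence about complementing other data concerns the IMU alone; UWB is described as a position reference. Nor does the SAP exclude sensor outcomes: it names no outcomes, so the gap is one of silence.
- The rule quoted concerns the TUG, a whole-task time, whereas the larger figures are for a 4 m walk whose use as an outcome is assumed. No document supports a 0.1 to 0.2 s shift; it shows sensitivity, not that bias will occur.
- It is tempting to replace the tester's TUG and TUG-COG totals with sensor times. Nothing shows that either instrument marks the start command or seat contact, so the documents do not establish that this is feasible.
- UWB appears only in the background. The visit text has participants put on the Walkasins and the IMU and does not mention the UWB tag.
- Fixed order, practice and participant expectation would be recorded faithfully by any sensor, and may be larger.

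What survives is narrower. The comparison is open, the tester can know the condition, and an independent record of walking is planned without being assigned to the comparison. Speed over a straight segment is the slope of position on time, which needs neither the start command nor seat contact.

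**Conclusion.** The concern holds in a limited form. The gait-speed result is exposed to tester timing bias, and the plan does not use recordings it describes that could check it. Under the assumed 4 m walk and 0.1 to 0.2 s shift, the false gain is about 0.02 to 0.05 m/s at 0.9 to 1.0 m/s. Whether that would look significant depends heavily on an SD that the documents do not give. The TUG is less affected. The documents do not support the stronger conclusions that such bias is present, that sensors could supply full TUG times, or that sensor timing would make the off/on contrast unbiased. The change is worth making because it is cheap and has most credibility if specified before data are seen.

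**What to change.** In Study Visit Procedures and the Statistical Analysis Plan:

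1. Confirm that the UWB tag and the IMU are worn and logged during both the off and the on assessments.
2. Prespecify walking speed over the straight segments (the SPPB walk and the TUG and TUG-COG walking legs) as an outcome in the paired comparison. Derive it by one fixed algorithm with stated rules for segment limits. Run it on files coded to hide on/off, with clock times and sequence removed, since order alone reveals the condition.
3. Keep the tester-recorded TUG and TUG-COG totals as they are. State how the SPPB walk is timed and over what distance.
4. Report the tester-minus-sensor difference by condition for the timed walk. A difference that changes between off and on would point to timing bias.
5. State that this addresses tester timing bias only, and that participant expectation, practice and the fixed off-then-on order remain.

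The cost is some extra data processing and SAP wording. Walks with lost signal will have no sensor value, and each sensor-derived speed carries random error of about 0.01 to 0.04 m/s over 4 m. It is somewhat larger on a single 10-foot leg: from end points at 0.9 m/s, the leg takes 3.05/0.9 = 3.39 s and the error is √2 × 0.1/3.39 = 0.042 m/s. If the UWB tag was not going to be worn during the assessments, wearing and logging it is an added step.

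### If the two TUG-COG tests use different fixed starting numbers, as in the protocol's example, number difficulty cannot be told apart from Walkasins off versus on; counterbalancing the numbers removes this cheaply

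*Combined protocol and SAP*

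**What the plan says.** Study Visit Procedures describes the TUG-COG as a Timed Up and Go walk while counting "backwards by threes from a randomly selected number between 20 and 100". For standardisation, the study replaces the random start with a fixed rule: the tester "will use the same starting number for all participants (e.g., the same odd number for the first TUG-COG assessment and the same even number" at the second). No numbers are named, and the odd/even pair is the only example.

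The same section fixes the order of conditions. Participants first "complete the following assessments with their Walkasins turned off and without the use of an assistive device". After a five-minute break and a repeat of the balance exercises, staff "retest participants on the same assessments with Walkasins turned on".

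The Statistical Analysis Plan states that "Walkasins on versus off conditions will be compared using paired t-test", with the Wilcoxon signed rank test for non-normal data. It also mentions regression to look at trends, but names no term for starting number. Participant Selection sets the size: "Up to 20 study participants will be enrolled in this pilot study". Pilot Study Aim and Hypothesis expects faster gait and better clinical outcomes with the device on, "suggesting less reliance on compensatory executive control".

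**The concern.** Using the same numbers for everyone is sensible, because a fresh random number at each test would add noise to the paired difference. The trouble is tying one number to the first test and another to the second. As the first test is always off and the second always on, number and device state then coincide for every participant. If one number is easier to count down from, the on/off difference in TUG-COG time absorbs that ease, for or against the device, and the data cannot reveal it afterwards.

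TUG-COG is the only listed measure that adds a cognitive task to walking. It therefore bears most directly on the idea that the device reduces reliance on executive control, in participants selected for mild cognitive impairment.

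**Working it through.** The documents give no significance level, SD, effect size or power calculation, so there is no planned figure to reproduce. The check has four parts.

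**1. Can the two effects be separated?** Let D be a participant's on-minus-off time. Write D = δ + γx + error, where δ is the on/off contrast, γ is the difference in seconds between the two numbers, and x is +1 or −1 according to which number was used with the device on. Under the protocol's example x = +1 for all 20 people. The columns for δ and γ are then identical (rank 1 of 2), and the mean of D estimates δ + γ. With a 10/10 counterbalance the rank is 2, and the average of the two group means estimates δ alone.

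**2. Could two numbers differ in difficulty?** As a rough marker, I counted how often a ten is crossed when subtracting threes from starts of 20 to 100, keeping the count non-negative. The marker is an assumption, not taken from the documents.

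| Subtractions | Odd/even pairs with unequal crossings |
|---|---|
| 3 | 328/1640 = 20% |
| 4 | 544/1640 = 33% |
| 5 | 856/1640 = 52% |
| 6 | 520/1640 = 32% |
| 7 | 320/1600 = 20% |
| 8 | 696/1482 = 47% |
| 9 | 632/1369 = 46% |
| 10 | 0/1260 = 0% |

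Unequal pairs differ by one crossing, and the odd and even averages differ by at most 0.22. Parity as such matters little; the particular numbers matter. The documents give neither the number of subtractions completed during a walk nor any link from crossings to seconds, so this table cannot be turned into a bias.

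**3. What would a number effect do to the paired t-test?** Assume no device or order effect, a two-sided 5% test and complete data. The statistic is noncentral t with n − 1 degrees of freedom and noncentrality γ√n/SD. For example, γ = 0.5 s, SD = 2 s and n = 20 give 0.5 × 4.472/2 = 1.118, critical value 2.093, rejection 18.6%.

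| n, SD of D (assumed) | γ = 0.1 s | 0.25 s | 0.5 s | 1.0 s |
|---|---|---|---|---|
| 20, 2 s | 5.5% | 8.3% | 18.6% | 56.5% |
| 20, 1.5 s | 5.9% | 10.9% | 29.4% | 80.7% |
| 20, 3 s | 5.2% | 6.5% | 10.9% | 29.4% |
| 15, 2 s | 5.4% | 7.4% | 14.7% | 43.8% |

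**4. What does counterbalancing achieve?** With a 10/10 split and a number term in the model (18 df), the number-related false-positive rate is exactly 5% for any γ under normal errors; simulation (100,000 runs per case, SD 2 s) gave 4.8% to 5.2%. A plain paired t-test on the same data is conservative, at about 3% when γ = 1.0 s, because the number effect inflates the SD of D. If the split is uneven, the unadjusted mean keeps a share of γ equal to the difference in group sizes over their sum: (11 − 9)/20 = 10%, or (12 − 8)/20 = 20%. The model term removes that too.

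**The case against.** The strongest reply is that no harm is shown. The alias biases the result only if the two numbers differ in a way that changes walking time, and nothing in the documents says they do. On the rough marker above, most odd/even pairs are equal at seven of the eight counts. A 0.1 s difference leaves the error rate close to nominal, and nothing in the documents supports 1.0 s. This stands: size and direction are unknown, and the rates are illustrations.

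Second, the odd/even pair is only an example. The rule could also mean one number at both tests, in which case difficulty cannot differ. That also stands, and the point is conditional on it. But that reading has participants rehearse the same sequence before the on test, so it brings its own bias.

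Third, the fixed off-then-on order is the larger problem, and balancing the numbers leaves it untouched. This is correct: after the change, an order effect of 0.5 SD would still produce rejection in about 56% of trials. The two problems are separate, however. The number problem can be removed even if the order is kept, and would need attention if the order were randomised.

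Fourth, matched numbers might do. Among starts of 30 to 100, 98 of 1,260 odd/even pairs (33 and 32, for instance) have equal crossings at every count from three to nine. That is simpler, but relies on an unproven marker of difficulty; counterbalancing does not.

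**Conclusion.** The concern holds, conditionally. Under the protocol's only example, or any scheme with a different fixed number at each test, starting number and device state coincide for everyone, and no analysis of the resulting data can separate them. That is a matter of design and needs no assumption. The consequence does: it could be negligible (5.2% to 5.9% rejection at 0.1 s) or serious (29.4% to 80.7% at 1.0 s), depending on a number effect and an SD that the documents do not give. It affects one of several outcomes in a pilot of at most 20 people and does not threaten the study as a whole. It is worth changing because the remedy costs almost nothing and must be in place before data are collected.

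**What to change.** - Choose two starting numbers, A and B, before enrolment and name them in the protocol.
- Using a pre-printed list randomised in blocks, have half the participants count from A when off and B when on, and half the reverse. If test order is also randomised, balance within order. Record the number used.
- For TUG-COG, regress the on-minus-off difference on number sequence coded +0.5/−0.5 and report the intercept as the on/off contrast.
- As the counterpart to the Wilcoxon signed rank test, take each participant's time with A minus time with B and compare the two sequences by rank-sum test. The number effect is common to both sequences, so they differ only through the on/off contrast.
- State in the report that this removes number difficulty only, and that practice, fatigue and period remain confounded with the device while the order is fixed.

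The cost is two form versions, a list, a short wording change and one residual degree of freedom. At n = 20 and SD 2 s, the 95% half-width goes from 2.093 × 2/√20 = 0.936 s to 2.101 × 2/√20 = 0.940 s, and power for a true 1.0 s difference from 56.5% to 56.2%. No extra participants or visits are needed.

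### Every participant is tested off first and on second, so the on-versus-off contrast cannot separate a device effect from an order effect

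*Combined protocol and SAP*

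**What the plan says.** Pilot Study Aim and Hypothesis sets out to study "the effect of lower-leg mechanical tactile sensory stimulation on the gait speed and balance function of participants with mild cognitive impairment", and reads a gain with the device on as a sign that walking needs less executive compensation. Research Design describes one session with a pre-post comparison in up to 20 people.

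Under Study Visit Procedures, participants put the device on, do the balance exercises and then "complete the following assessments with their Walkasins turned off and without the use of an assistive device". These are the SPPB, TUG and TUG-COG. After a five-minute break, "study staff will then guide the participants through the same sensory integration exercises they performed before the first set of assessments", and then: "Participants will then retest participants on the same assessments with Walkasins turned on and without the use of assistive devices". No randomised or alternated order, repeat off test, sham or masking is described.

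For the TUG-COG, the example given is "the same odd number for the first TUG-COG assessment and the same even number for the second TUG-COG assessment". Before any of this there is a four-metre eligibility walk, of which the protocol says "This test may be repeated if necessary". The Falls Efficacy Scale is completed once, at the end, so it has no on-off contrast.

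The Statistical Analysis Plan compares on with off by paired t-test, or by Wilcoxon signed-rank test for non-normal data, with Shapiro-Wilk as the normality check. It also mentions regression without naming its terms. No order term and no limitation about order appears.

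**The concern.** When everyone goes from off to on, anything that changes between the first and second set is counted as the device. Familiarity with the tasks and a second round of exercises would favour on; tiredness would favour off. Expectation is in the contrast too, because the inclusion criteria require that participants can feel the vibration.

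A gain could therefore appear with no stimulation effect, and net fatigue could hide a real one. A larger sample or a different test does not help, because the problem is what is being estimated, not how precisely. It matters because the aim is causal, and because Potential Benefits hopes the data will inform the device's place in treating gait difficulty in mild cognitive impairment.

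**Working it through.** The documents give no power, alpha, SD or effect size, so there is no figure of theirs to reproduce.

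**Inputs.** From the documents: n up to 20, fixed off-then-on order, paired tests. Assumed: two-sided 5%, and all shifts in SDs of the paired difference, oriented so that positive means better.

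**1. Can order be separated?** Take 20 participant intercepts, an on/off column and a second-set column: 22 columns. Under fixed order the last two columns are identical and the rank is 21. With 10 participants in each order the rank is 22. Adding an expectation column makes 23 columns and leaves the rank at 22, so expectation is not separated either way.

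With stimulation effect δ, expectation e and net order effect π, the fixed-order contrast has mean δ + e + π. Only the sum is estimable, whatever terms the regression contains.

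**2. Order effect alone (δ = e = 0).** For the paired t-test the noncentrality is d√n. At n=20, df is 19 and critical t is 2.093. For d=0.3, 0.3 × √20 = 1.342.

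| Order shift d (SD) | 0 | 0.1 | 0.2 | 0.3 | 0.5 |
|---|---|---|---|---|---|
| P(p<0.05), n=20 | 5.0% | 7.1% | 13.6% | 24.7% | 56.5% |
| P(p<0.05), n=10 | 5.0% | 5.9% | 8.8% | 13.6% | 29.3% |

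**3. Does the choice of test help?** Simulation, 20,000 runs, n=20. The gated rule is paired t, or Wilcoxon if Shapiro-Wilk p<0.05. The heavy-tailed case is t(3) scaled to unit SD.

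| Differences, test | 0 | 0.2 | 0.3 | 0.5 |
|---|---|---|---|---|
| Normal, Wilcoxon | 5.0% | 13.0% | 23.3% | 54.6% |
| Normal, gated | 5.3% | 13.8% | 24.6% | 56.8% |
| t(3), Wilcoxon | 4.9% | 21.6% | 41.0% | 78.4% |
| t(3), gated | 5.0% | 21.2% | 39.8% | 76.3% |

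The rates depend on the distribution, but neither test removes the bias.

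**4. Order effect against the device.** With n=20, 80% power needs δ = 0.66 SD. Opposing shifts of 0.2, 0.3 and 0.5 leave 0.46, 0.36 and 0.16 SD, and power of 49.8%, 33.4% and 10.5%.

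**5. Randomised order, 10/10.** Let λ be carry-over from on into a later off set, and leave expectation aside. The mean second-minus-first change is δ + π in the off-on sequence and −δ + π + λ in the on-off sequence. Half the difference is δ − λ/2, and π cancels. The SE is √[(SD²/10 + SD²/10)/4] = SD/√20 = 0.224 SD, the same as under fixed order, with df 18 instead of 19. With no effect and no carry-over, at order shifts of 0, 0.3 and 0.5, simulated false positives were 4.9–5.1% (t) and 4.1–4.4% (rank-sum) for normal differences, and 4.2–4.5% and 4.3–4.4% for t(3).

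**6. The carry-over trade-off.** Fixed-order bias is π; randomised-order bias is −λ/2. Randomised order is closer to the truth when λ < 2|π|:

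- π = 0.3 allows λ up to 0.6, and 0.6/0.66 = 91% of the effect.
- π = 0.1 allows λ up to 0.2, and 0.2/0.66 = 30% of the effect.

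Half carry-over (λ = 0.33) gives 0.66 − 0.165 = 0.495 SD and 55.4% power. Full carry-over (λ = 0.66) gives 0.33 SD and 28.8%. A sequence test on within-person sums, at an assumed within-person correlation of 0.7–0.9, would detect these only 5.3–6.0% and 6.2–9.0% of the time.

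**The case against.** This is an openly declared pre-post pilot with hedged language and no alpha, success criterion or go/no-go rule, so false-positive rates borrow a decision rule that the protocol does not state. Every shift above is assumed, and at 0.1 SD the rate is 7.1% against 5%. The simulations use continuous differences and do not model a composite score such as the SPPB. The break may limit fatigue, and the eligibility walk gives some prior exposure to timed walking. Off-first also avoids carry-over. The documents do not show that five minutes is an adequate washout, and the conclusion of the cross-over study quoted in Summary of Previous Walkasins Research, that the cues are taken up into motor control, makes carry-over arguable. The risk section says that the device may distract walkers, and on-first removes an unstimulated first run. Randomising would still leave expectation in place.

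Much of this stands. The size of the bias is not established, and choosing between fixed and randomised order means weighing two unknown biases. But the pilot label describes the design; it does not limit what a gain may be attributed to, and the confounding does not depend on any p-value rule. The eligibility walk does not rescue the contrast. It comes before the device and exercises, it selects slow walkers (so regression to the mean enters), and it has no counterpart for the TUG, the TUG-COG or the rest of the SPPB.

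Two side points carry less weight. The TUG-COG numbers are only an example, and nothing shows that they differ in difficulty. The protocol text does not say whether the device is on during either exercise block, but Pilot Study Duration says "A flow chart of the study visit appears on the following page", and that chart was not in the text available to me.

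**Conclusion.** The concern holds. For the SPPB, TUG and TUG-COG, condition and order are the same variable, and no analysis of these data can separate them without an outside or untestable assumption. That conclusion follows from the design and needs no numerical assumption.

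The practical size is unknown. The percentages show what would follow from given order shifts under the stated assumptions; they do not predict this trial's error rate. This is a design choice that should be fixed, not an internal contradiction. Following the plan as written could credit the stimulation with a change that it did not cause, or miss one that it did.

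**What to change.** **Minimum, if the fixed order stays.** Describe the result as second (on) versus first (off) set, list order and expectation as unseparated, and do not attribute gains to the stimulation. This costs wording only.

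**Preferred.**

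- Randomise participants about 1:1, from a blocked list, to off-then-on or on-then-off, with the same exercises and break.
- Keep the TUG-COG starting number tied to occasion; it is then balanced across conditions.
- In the SAP, report half the between-sequence difference in mean second-minus-first change, with a 95% CI. For non-normal data, use the rank-sum test of those changes between sequences.
- State the no-carry-over assumption, do not justify it with a sequence test, and give the first-set comparison between sequences descriptively.
- Say that expectation effects remain.

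Under either option, state the device state during each exercise block if the flow chart does not already do so.

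**Cost of randomising.**

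- A protocol and SAP amendment with IRB review, which should also consider testing with the device on first, since the planned spotter is described without reference to order.
- A check of the consent form if it describes the order, and a 20-line list. No extra visit, test or staff.
- One degree of freedom: critical t 2.101 against 2.093, a CI about 0.4% wider (2.101/2.093 = 1.004). A 9/11 or 8/12 split gives 79% or 78% power at 0.66 SD.
- Rank-sum against signed-rank power at 0.66 SD: 75% against 78% for normal differences, 91% against 93% for t(3).
- Exposure to carry-over, as quantified above.

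The randomised cross-over of this device cited in the protocol shows that order can be varied. It was done in sensory peripheral neuropathy, which this trial excludes, so it does not show that carry-over is absent here.
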